**Additional request details**

M	Primary Endpoint/ objective is safety	No
M	Study exploring new combinations, alternative dosing/dosing schedules or new formulations	No

M	Study with clinical pharmacology objectives, including biomarker, pharmacokinetic (PK) or pharmacodynamics (PD) evaluations	No
O	Author	[name], PhD Institut Bergonie Early Phase Trials and Sarcoma Units [name] Phone: [name] Fax: [name] E-mail: [contact]
O	Investigator Operations Manager email	[name], PhD  Head of Clinical Research Unit: [name] Institut Bergonié – Bordeaux Phone :[name] E-mail : [contact]
M	Study support	Financial
M	Study is financially supported by other organizations	No

Rationale and objectives	
O	Please explain why this study is non-blinded (if applicable): This is a retrospective study.
M	Study Type and Design  This multicenter, retrospective study has a primary objective to assess the impact of NTRK gene fusions on the PFS of first-line systemic therapy for the treatment of locally advanced/unresectable or metastatic solid tumors.  Control subjects will be matched based on the characteristics of the NTRK fusion study population to the greatest extent possible.
M	Rationale  The tropomyosin receptor kinase (Trk) receptor family comprises 3 transmembrane proteins referred to as Trk A, B and C (TrkA, TrkB and TrkC) receptors that are encoded by the NTRK1, NTRK2 and NTRK3 genes, respectively. These receptor tyrosine kinases are expressed in human neuronal tissue and play an essential role in the physiology of development and function of the nervous system through activation by neurotrophins. Gene fusions involving NTRK genes lead to transcription of chimeric Trk proteins with constitutively activated or overexpressed kinase function conferring oncogenic potential. These genetic abnormalities have recently emerged as targets for cancer therapy, because novel compounds have been developed that are selective inhibitors of the constitutively active rearranged proteins. Developments in this field are being aided by next generation sequencing methods as tools for unbiased gene fusions discovery. However, the incidence

	of NTRK aberrations in solid tumors is unknown as well as the natural history of NTRK-rearranged tumors.

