M	
Primary Study Objective
 
To assess retrospectively the effect of NTRK gene fusions on the progression free survival (PFS) of first-line systemic therapy for the treatment of locally advanced/unresectable or metastatic solid tumors

O	
Secondary Study Objectives
 
 
• To evaluate the frequency of NTRK gene fusions in subjects with locally advanced/unresectable or metastatic solid tumors.
 
• To assess the treatment outcome to first-line anti-cancer therapy in terms of objective response rate (ORR), duration of response (DOR), and overall survival (OS) in subjects with locally advanced/unresectable or metastatic solid tumors with NTRK gene fusions.
 
• To explore possible demographic characteristics prevalent in subjects with locally advanced/unresectable or metastatic solid tumors and NTRK gene fusions.
 
• To explore the frequency and treatment outcome interaction of concomitant genetic alterations.
 
• To look for trends in the data that may suggest relationships between covariates of interest and treatment outcome in subjects with locally advanced/unresectable or metastatic solid tumors harboring NTRK gene fusions.
 

M	
Study operational/organizational aspects
 
This will be a multicenter, retrospective study. Institut Bergonié as the Sponsor of this study, will be responsible for getting regulatory approvals, selecting the investigational sites, capturing study data in an appropriate data base

Population and methods	
M	
Study Population
 
Adult and pediatric patients with locally advanced/unresectable or metastatic solid tumors

M	
Inclusion Criteria (detailed)
 
For inclusion of a subject in the study population, all of the following criteria must be fulfilled:
 
 
1. Age <math>\geq</math> 1 month.
 

2. Subject has/had a histologically or cytologically confirmed diagnosis of solid tumor including but not exclusively: soft tissue sarcoma, BRAF wild type melanoma, KRAS wild-type colorectal cancer, central nervous system, EGFR-wild type non-small cell lung cancer.

3. Subject has locally advanced/unresectable or metastatic disease.

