4. Subject has received at least one systemic anti-cancer therapy for locally advanced/unresectable or metastatic disease for which there is available outcome information in terms of PFS, or the latter can be estimated based on the subject's records.

5. Subject has tumor material available for immunoscreening (IHC for NTRK gene fusions).

6. Written and voluntary informed consent understood, signed and dated, or a waiver of consent is granted according to French regulations

Subjects who are tested positive by IHC (Pan-Trk IHC testing with mAb EPR17341) will be the subject of molecular assays such as next-generation sequencing (Archer Dx fusion assay) of tumor material [parrafin embedded material]), so that tumor harboring *NTRK1*, *NTRK2* or *NTRK3* gene fusions, is identified properly.

After identification of the NTRK fusion study population, control subjects with locally advanced/unresectable or metastatic solid tumors, who do not have NTRK fusions will be selected in an attempt to closely match NTRK fusion subjects.

M	
Exclusion Criteria
 
The following exclusion criterion should be considered:
 
Subjects who have not yet received or completed at least one systemic anti-cancer therapy for locally advanced/unresectable or metastatic cancer.

M	
Test Treatment(s) (Description)
 
n/a
 
.

O	
Test Treatment(s) or Investigated Treatment(s): Rationale for unusual or novel approaches
 
n/a

M	
Request for Study Drug Supply
 
No

M	
Reference Treatment or Modality/Treatment or Modality of Comparison (Description)

	n/a
--	-----

Safety reporting	
M	Safety reporting (valid for clinical studies only) n/a

Statistical analysis	
O/M	Standard of Reference/Standard of Truth n/a
M	Rationale for selection of a reference treatment n/a
M	Assignment of subjects to study arms or groups (Randomization/Stratification) n/a (this will be a retrospective study)
M	Blinding n/a
M	Concomitant Treatment(s) n/a
M	Primary Outcome Progression-free survival observed with first-line anti-cancer therapy

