	Collection of Treatment Information: 
 
• Prior/current surgical treatments for cancer. 
 
• Dates of surgeries
 
 
 
• Prior/current radiological treatments for cancer. 
 
• Anatomical sites.
 
• Dates of radiation treatments
 
 
 
• First line systemic treatment for locally advanced/unresectable or metastatic cancer: 
 
• Dates of treatment (start, end).
 
• Performance status at the time of first line therapy for treatment of recurrent or metastatic disease.
 
• Treatment outcome (response and response criteria).
 
• Date of progression(s) (progression criteria).
 
 
 
• Other prior/current systemic treatments for cancer. 
 
• Dates of treatment (start, end).
 
• Treatment outcome (response and response criteria).
 
 
 
• Date of progression(s) (progression
 
		X

	
criteria)
 
 
• Date of death (if any) and cause of death
 
 
Collection of NTRK fusion Information:
 
 
• Anatomical biopsy sample site (including blood/urine sample). Date of sampling and setting (initial diagnosis, locally advanced/unresectable or metastatic disease)
 
• Matrix (tumor biopsy, blood, urine)
 
• Tumor histology (from biopsy sample or primary diagnosis)
 
• NTRK fusion in sample. Allele frequency (if available); this information is not applicable for control subjects.
 
• Other relevant mutations or genetic alterations, if available. Allele frequencies (if available)
 
• Test platform (e.g. NGS). Mutations tested (PCR methods) or exons sequenced (sequencing methods).
 
		
			X
M	
Follow-up period
 
n/a
		

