M	
Statistical & Analytical Plan and Methodology
 
The primary objective of this descriptive study is to determine if there are statistically significant differences in PFS to first line systemic therapy between subjects with recurrent/metastatic disease and NTRK fusion versus those without a known NTRK fusion.
 
The two groups will be matched with respect to histological subtype, sex, age (+/-5 years), and pathological tumor-node-metastasis (TNM) stage.
 
The Kaplan-Meier method will be employed for the analysis of PFS. A nonparametric test, such as the log-rank test, based on the Kaplan-Meier estimator for survival curves, will be employed to assess the association between PFS and the presence of NTRK fusion. In addition, predictive modeling, including Cox proportional hazards models with NTRK fusion as a predictor may also be used to estimate the relative risk of the exit-event of subjects with tumors with NTRK fusion versus subjects with tumors without known NTRK fusion. If the data allow it, other types of predictive modeling may also be explored. If the proportionality of hazard assumption fails, then parametric approaches will be used.
		

	
Given the rarity of NTRK fusions among subjects with solid tumors, the sample size for this study will not be driven by powering the study. A post hoc power calculation will be provided. Clinically relevant changes will be defined as increases in median survival times that are greater than 30%, regardless of confidence interval width.
 
An assessment of the impact of certain covariates will be conducted by comparing their associated hazard ratios from the Cox proportional hazard (or parametric model) analysis.
 
Descriptive statistics will be employed to define demographic and treatment outcome, as well as overall frequency of NTRK fusions in the screened population. This will include exploration of potential effects on subject's treatment outcomes of different forms of NTRK fusions and of other genetic alterations.

--	--

Timelines	

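### Controls are defined and matched without regard to other driver alterations, and item 2 does not say whether wild-type status is required

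*Combined protocol and SAP*

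**What the plan says.** The study population is "Adult and pediatric patients with locally advanced/unresectable or metastatic solid tumors", with no molecular restriction. Item 2 of Inclusion Criteria (detailed) then describes the eligible solid tumours as "including but not exclusively: soft tissue sarcoma, BRAF wild type melanoma, KRAS wild-type colorectal cancer, central nervous system, EGFR-wild type non-small cell lung cancer". Item 4 of the same section accepts any type of first-line treatment: "Subject has received at least one systemic anti-cancer therapy for locally advanced/unresectable or metastatic disease". The only exclusion criterion is "Subjects who have not yet received or completed at least one systemic anti-cancer therapy for locally advanced/unresectable or metastatic cancer".

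Controls are drawn after the fusion cases are identified. They are patients "who do not have NTRK fusions will be selected in an attempt to closely match NTRK fusion subjects". Study Type and Design states the general intention: "Control subjects will be matched based on the characteristics of the NTRK fusion study population to the greatest extent possible". The operative list is in Statistical & Analytical Plan and Methodology: "The two groups will be matched with respect to histological subtype, sex, age (+/-5 years), and pathological tumor-node-metastasis (TNM) stage".

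Under Visit schedule, the data collected include "Other relevant mutations or genetic alterations, if available. Allele frequencies (if available". The statistical section tests PFS by a log-rank type of test and makes a Cox model optional. It plans to look at covariates it does not name and to explore other genetic alterations descriptively.

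**The concern.** The primary question is what an NTRK fusion does to PFS on first-line therapy. Other drivers can determine which first-line drug a patient receives and can carry prognostic weight of their own. The plan seems to accept this: item 2 singles out three markers, and a secondary objective concerns how concomitant alterations interact with treatment outcome. The control rule takes none of it forward.

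If drivers are unevenly distributed between the two groups, the comparison is no longer fusion against no fusion. It becomes fusion against a mixture of patients with no driver and patients with some other driver, possibly on a different class of drug. The sign could vary by histology. A driver that brings an effective targeted drug lengthens control PFS and makes the fusion look harmful. A driver that worsens prognosis does the reverse.

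**Working it through.** **Step 1: who can be a control.** Two readings of item 2 are possible.

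| | Wild-type terms are examples | Wild-type terms are requirements |
|---|---|---|
| BRAF-mutant melanoma, KRAS-mutant colorectal, EGFR-mutant lung | eligible | not eligible |
| Other drivers in those three tumour types | eligible | eligible |
| Any driver in any other solid tumour | eligible | eligible |

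Only the first row changes. The exclusion criterion and the control definition remove none of the patients in the lower two rows.

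**Step 2: does matching or analysis deal with it?** The four matching factors include no marker and no treatment. The log-rank comparison has no stated adjustment. The Cox model is optional, with covariates unnamed. The descriptive look at other alterations does not alter control selection or the primary test. Among the data items, the alteration field is the one that can identify these controls. The sub-items under first-line treatment cover dates, performance status, outcome and progression, and do not name the drug.

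**Step 3: scale.** The plan gives no driver prevalence, PFS median, event count or power calculation, so there is no figure of its own to reproduce. The inputs below are assumptions:

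- no true fusion effect, and exponential PFS without censoring;
- median 6 months in fusion cases and in driver-negative controls;
- median *m* = 12 or 18 months in a share *p* of controls;
- no such drivers among fusion cases.

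The control median *t* solves (1 − *p*)·2^(−*t*/6) + *p*·2^(−*t*/*m*) = 0.5.

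Check for *p* = 0.20, *m* = 12, *t* = 6.79: 0.365 + 0.135 = 0.500.

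| Share *p* | *t*, *m* = 12 | *t*, *m* = 18 | Control median longer by |
|---|---|---|---|
| 10% | 6.38 | 6.55 | 6-9% |
| 20% | 6.79 | 7.20 | 13-20% |
| 40% | 7.77 | 8.86 | 29-48% |

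A control median 30% longer is reached at *p* of about 41% (*m* = 12) or 28% (*m* = 18).

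On the hazard scale, *m* = 12 means a hazard ratio of 6/12 = 0.5 for affected controls. The large-sample Cox hazard ratio for fusion against control is then 1.09 at a 10% share, 1.18 at 20% and 1.27 at 30%, where the truth is 1.0.

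**Step 4: dependence on imbalance.** If fusion cases carried the same drivers in the same share and with the same effect on PFS, both groups would follow the same mixture. The medians would then be equal and the bias zero.

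**The case against.** The strongest reply concerns item 2. The open-ended wording may only extend the list to further tumour types, with melanoma, colorectal and lung cancer entering as wild type; otherwise the three qualifiers do no work. A reader might infer that EGFR-mutant lung, BRAF-mutant melanoma or KRAS-mutant colorectal patients are definitely eligible as controls. The documents do not settle that, and on the stricter reading all three are ineligible. This part of the objection stands. It narrows the point but does not remove it, as the lower rows of the first table show.

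The premise that fusion cases seldom carry other drivers is also not in the documents, which treat concomitant alterations as an open question. The shares and medians above are assumed and run in one direction only. Matching on histology ties the control mix to that of the cases, and the list includes sarcoma and central nervous system tumours, so a large affected share across all controls cannot be presumed. All of this stands.

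A reader might further infer that the fusion group would look worse by more than the plan's 30% margin. The margin is worded as an increase in median survival. Expressed as a fusion deficit, the illustration gives 1 − 6/6.79 = 12% to 1 − 6/7.20 = 17% at a 20% share, and 23% to 32% at 40%. Only the extreme corner passes 30%.

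Finally, the general promise of close matching and the optional covariate modelling could accommodate driver status. They commit to nothing specific, so they do not close the gap.

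**Conclusion.** The point holds as a gap in control selection and analysis. Item 2 is ambiguous, and on either reading a control may carry another driver, with no matching factor or prespecified adjustment to handle it. The primary log-rank comparison would credit any resulting PFS difference to the fusion.

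Neither the size nor the direction of the bias can be derived from the documents. Under the stated assumptions it is small when about a tenth of controls are affected and material when about a third or more are. It requires such drivers to be less common in fusion cases. This is a weakness worth correcting before controls are chosen; it does not show that the comparison will be biased by any given amount.

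**What to change.** 1. In item 2, state whether the BRAF, KRAS and EGFR wild-type terms are requirements, and that the answer applies to both cases and controls.
2. Add to the matching list in Statistical & Analytical Plan and Methodology: same recorded status for the named marker (BRAF in melanoma, KRAS in colorectal cancer, EGFR in non-small cell lung cancer), where known.
3. Prespecify two sensitivity analyses of the primary PFS comparison. The first excludes, from both groups, patients with another recorded driver alteration, using a list fixed before control selection. Applying it to controls alone would create a new asymmetry. The second excludes matched sets in which status is unknown.

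The changes use the alteration field already on the form, and controls come from a screened pool of about 3,700. The cost is somewhat fewer eligible controls in a few histologies. Status will also be incomplete, because alterations are recorded only where available. The sensitivity analyses will therefore reduce the confounding without eliminating it, and the number of patients with unknown status should be reported for each group.

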M	
Planned Study Timelines:
 
 
1. Enrolment rate (patients per month): 300 patients/months
 
2. Planned estimate of treatment duration: not applicable
 
3. Submission date to health authority/ethics: not applicable
 
4. Start of subject enrolment: December 2018
 
5. End of Subject enrolment: December 2019
 
6. All patients completed: December 2019
 
7. End of Study: March 2020
 
8. Report (as described in the contract): Report every 3 months
 
9. Planned publication/presentation: June 2020
 

Limitations	
O	
Criteria for selection of evaluable cases:
 
All patients:
 
who have received at least one systemic anti-cancer therapy for locally advanced/unresectable or metastatic disease for which there is available outcome information in terms of PFS,
 
who have tumor material tested by IHC for NTRK gene fusions,
 
will be included in the analysis.

M	Interim Analyses (if applicable)

	
Interim analyses will be the subject of periodic reports based upon collection of data on first 1,000, 2,000 patients and a final analysis will be conducted after completion of the whole data set analysis.
 
At each interim analyses, the proportion of NTRK-rearranged cases will be estimated in order to assess the feasibility of a comparative analysis with matched controls.

M	
Number of Evaluable Patients (estimate): it is anticipated to collect data on 3,700 patients

M	
Sample Size Assumptions/Target Number of Valid Cases (incl. Power and Confidence)
 
No sample size estimate has been calculated. It is assumed that a sample size of 3,700 patients should be sufficient to address the primary objective of this study.

0	
Statistical analyses
 
 
Quantitative variables will be described using mean and standard deviations if the normality assumption is satisfied, else other descriptive statistics (median, range, quartiles) will be reported.
 
Qualitative variables will be described using frequency, percentage and 95% confidence interval (binomial law).
 
Survival endpoints will be analysed using the Kaplan-Meier method. The median survival rates will be reported with a 95% confidence interval. Median follow-up will be calculated using the reverse Kaplan-Meier method.
 

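### Only IHC-positive tumours are described as going on to sequencing, so the reported NTRK fusion frequency estimates true frequency times IHC sensitivity and is biased downward unless that sensitivity is 100%

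*Combined protocol and SAP*

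**What the plan says.** All places are in the combined protocol and SAP.

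- **Target.** Secondary Study Objectives: "To evaluate the frequency of NTRK gene fusions in subjects with locally advanced/unresectable or metastatic solid tumors". Secondary Outcomes names the same quantity.
- **Test pathway.** Inclusion Criteria (detailed): "Subjects who are tested positive by IHC (Pan-Trk IHC testing with mAb EPR17341) will be the subject of molecular assays such as next-generation sequencing". The group named for this step is "Subjects who are tested positive by IHC", and this is the only confirmation pathway described. Neither all IHC-negative tumours nor a sample of them is said to be sequenced.
- **Denominator.** Statistical & Analytical Plan and Methodology refers to the "overall frequency of NTRK fusions in the screened population". Criteria for selection of evaluable cases asks for patients "who have tumor material tested by IHC for NTRK gene fusions"; a sequencing result is not required.
- **Interval.** Statistical analyses: "Qualitative variables will be described using frequency, percentage and 95% confidence interval (binomial law").
- **Size.** Number of Evaluable Patients: "it is anticipated to collect data on 3,700 patients".
- **Test accuracy.** The item on the standard of reference or truth is marked not applicable. No IHC sensitivity, correction for missed fusions or caveat on the frequency is given.

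**The concern.** A tumour that carries a fusion but stains negative stays in the denominator and has no described route into the numerator. Molecular confirmation removes IHC false positives, so they do not offset the fusions that IHC misses. The estimator therefore targets the frequency of IHC-positive, confirmed fusions but carries the label of fusion frequency. The binomial interval covers sampling error only and takes no account of missed cases.

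The frequency is a secondary, descriptive outcome, but it is not incidental. The Rationale gives the unknown incidence of NTRK aberrations as a reason for the study, and the Interim Analyses item uses the estimated proportion to judge whether the matched comparison is feasible. A reader who takes the published interval at face value would treat it as a 95% interval for all fusions in the screened population. The plan gives no basis for that.

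**Working it through.** **Plan's own figure.** There is none to reproduce. No prevalence, sensitivity or interval width is stated for the frequency, and no sample size was calculated.

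**Inputs**
- n = 3,700, from Number of Evaluable Patients.
- True frequency p: not given. Assumed 0.3%, 0.5% and 1%.
- IHC sensitivity Se: not given. Assumed 75% to 100%.
- The confirmatory assay is taken as error-free.
- The plan says only that the interval is binomial; the exact (Clopper-Pearson) form is used here.

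**Step 1: what is estimated.** The number of confirmed cases is X ~ Binomial(n, p × Se), so the expected value of X/n is p × Se. The relative shortfall is 1 − Se whatever the value of p: 5% at Se = 95% and 25% at Se = 75%.

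**Step 2: coverage.** For each possible count x, compute the exact 95% interval, then add P(X = x) over all x whose interval contains p.

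At n = 3,700 and p = 0.5%, for example, the interval contains p when x is 11 to 27. With Se = 100%, 3,700 × 0.005 = 18.5 cases are expected and coverage is 95.3%. With Se = 75%, 18.5 × 0.75 = 13.9 are expected and P(11 ≤ X ≤ 27) = 81.6%. The whole interval lies below the truth in 18.4% of studies.

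Coverage of the true p by the nominal 95% interval:

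| Assumed Se | Understated by | p = 0.3% | p = 0.5% | p = 1% |
|---|---|---|---|---|
| 100% | 0% | 96.7% | 95.3% | 95.3% |
| 95% | 5% | 96.8% | 95.0% | 94.4% |
| 90% | 10% | 96.4% | 93.6% | 91.3% |
| 85% | 15% | 95.4% | 91.0% | 85.7% |
| 80% | 20% | 93.9% | 87.1% | 77.1% |
| 75% | 25% | 91.7% | 81.6% | 65.6% |

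The exact interval is conservative, so some entries exceed 95%. Coverage falls with lower Se and, below 95% Se, with higher p, because at higher p the interval is narrower relative to the bias.

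**Step 3: what the scaled table would show.** Suppose 14 cases are confirmed: 14/3,700 = 0.38%, exact interval 0.207% to 0.634%. Dividing by Se:

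| Assumed Se | Estimate | 95% interval |
|---|---|---|
| 100% | 0.38% | 0.21% to 0.63% |
| 90% | 0.42% | 0.23% to 0.70% |
| 75% | 0.50% | 0.28% to 0.85% |

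**The case against.** The strongest case against is that the effect may be nil or trivial.

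- **Sensitivity may be high.** At 95% coverage is essentially nominal, and at a true frequency of 0.3% it stays above 95% down to 85%. This stands. A reader might infer that the planned interval is too low as a matter of fact, but the documents give no sensitivity and support only the conditional statement.
- **Sampling error is often larger than the bias.** With 14 cases the half-width is about 56% of the estimate, against a 25% bias at the low end of the assumed range, and the interval still contains 0.5%. This also stands, but it does not mend the label, and at 1% true frequency the loss of coverage is no longer small.
- **The plan is open about its pathway.** It refers to the screened population and describes the comparison group as having no known fusion. That allows for undetected fusions among controls, although Inclusion Criteria (detailed) says controls do not have fusions. Neither phrase qualifies the frequency itself.
- **Dividing by an assumed sensitivity adds no trial data.** True; the table shows how far the conclusion depends on an unverified assumption, and should say so.

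Two further readings go too far. The estimate is not a lower bound for all fusions: a point estimate with sampling error is not a bound. The inclusion list also names BRAF-, KRAS- and EGFR-wild-type tumours, so the direction of any difference from solid tumours in general is unsettled. Nor does the data form clearly provide an internal check. It records other alterations only where available, marks the NTRK fusion item as not applicable to controls, and any such results would come from a selected subset.

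**Conclusion.** The point holds in conditional form, as a low-cost improvement in reporting. As described, the plan estimates true frequency times IHC sensitivity in the screened population and labels it fusion frequency. The bias is downward unless sensitivity is 100%, and the plan offers no means of quantifying it. Over assumed sensitivities of 75% to 95% and true frequencies of 0.3% to 1%, coverage lies between 65.6% and 96.8%.

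This rests on three assumptions: the single pathway described is the one followed, the confirmatory assay makes no errors, and the evaluable number is 3,700. Sequencing failures on paraffin material, if counted as negative, would add to the downward bias; the plan does not say how they are counted. The conclusion concerns the screened population only.

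**What to change.** 1. Name the endpoint *frequency of IHC-positive, assay-confirmed NTRK fusions in the screened population* in the objectives, the outcomes and the statistical section.
2. State that it is expected to understate the frequency of all fusions in that population if IHC misses any, and that IHC sensitivity is not measured in this study.
3. Add one table dividing the estimate and both confidence limits by a pre-stated sensitivity range, for example 75% to 100%, marked as an assumption.

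This costs one relabelled endpoint, a sentence and a table, with no new assays, patients or data fields. The price is a narrower claim and a wider stated range. Sequencing a small sample of IHC-negative tumours would not be a good substitute: no positives among 500 gives a one-sided 95% upper limit of 1 − 0.05^(1/500) = 0.6% for the missed rate, which is as large as the frequencies considered here.

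### The exclusion of patients who have not yet completed a systemic therapy, read naturally, drops progression-free patients still on first-line treatment instead of censoring them, which biases median PFS downward and shrinks any true difference

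*Combined protocol and SAP*

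**What the plan says.** Three places in the combined protocol and SAP decide who enters the PFS analysis.

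- **Exclusion Criteria.** Under the lead-in "The following exclusion criterion should be considered", the only criterion is: "Subjects who have not yet received or completed at least one systemic anti-cancer therapy for locally advanced/unresectable or metastatic cancer".
- **Inclusion Criteria, item 4.** "Subject has received at least one systemic anti-cancer therapy for locally advanced/unresectable or metastatic disease", continuing "for which there is available outcome information in terms of PFS, or the latter can be estimated" from the records. There is no completion condition.
- **Criteria for selection of evaluable cases.** All patients are analysed "who have received at least one systemic anti-cancer therapy for locally advanced/unresectable or metastatic disease", again "for which there is available outcome information in terms of PFS", provided their tumour was tested by IHC. There is no completion condition, and item 4's allowance for estimated PFS is absent.

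The primary outcome is PFS on first-line therapy. It is analysed by Kaplan-Meier and a log-rank test, with Cox modelling as an option. Median follow-up is to be obtained by reverse Kaplan-Meier. The timeline lists "All patients completed: December 2019" but does not call this the PFS cut-off, and the follow-up period is marked not applicable.

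**The concern.** The word *completed* appears as a therapy condition only in the exclusion, without a definition. Combined with *not yet*, it most naturally describes a patient whose therapy is still running. Such patients are foreseeable: enrolment runs to December 2019, no latest first-line start date is set, and the data collection lists current as well as prior treatments.

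When therapy continues until progression, a patient still on a first therapy is one who has not progressed. Removing that patient conditions eligibility on the outcome. Short PFS times are kept in full and long ones are kept only if therapy began early enough. The loss is greater in the group with longer PFS, so a true difference is attenuated.

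Two results are at stake: the absolute PFS medians, in a study whose rationale is that the natural history of these tumours is unknown, and the size of any true difference. The Statistical & Analytical Plan calls an increase in median survival above 30% clinically relevant whatever the width of the confidence interval. If that rule is applied to PFS, a shrunken ratio enters it directly.

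**Working it through.** The plan contains no PFS, event or power figure to reproduce. The check therefore asks what the natural reading does under stated assumptions.

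**Assumptions (none is in the documents).** PFS is exponential. The control median is 8 months. The fusion median is 10.4 (ratio 1.30, HR 8/10.4 = 0.77) or 12 (ratio 1.50). Time from first-line start to cut-off is uniform on 0 to W months, the same in both groups. Therapy runs until progression.

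**Excluded share.** With l = ln 2 / median, the share still on therapy at cut-off is (1 − exp(−lW)) / (lW). For controls and W = 24: l = 0.0866, lW = 2.079, so (1 − 0.125)/2.079 = 0.421.

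**Median of those kept.** The kept PFS times have density proportional to l·exp(−lt)·(1 − t/W) on 0 to W. The kept median solves F(t) = F(W)/2, where F(t) = (1 − e^(−lt)) − [(1 − e^(−lt))/l − t·e^(−lt)]/W. For controls and W = 24, F(W) = 0.579 and t = 4.40 months.

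| W (months) | Excluded, control | Excluded, fusion (10.4) | Control median (true 8) | Fusion median (true 10.4) | Ratio (true 1.30) | Ratio (true 1.50) | HR (true 0.77) |
|---|---|---|---|---|---|---|---|
| 24 | 42% | 50% | 4.40 | 4.87 | 1.11 | 1.16 | 0.91 |
| 36 | 31% | 38% | 5.38 | 6.18 | 1.15 | 1.23 | 0.88 |
| 60 | 19% | 25% | 6.38 | 7.68 | 1.20 | 1.32 | 0.84 |
| 120 | 10% | 13% | 7.21 | 9.05 | 1.26 | 1.41 | 0.80 |
| 180 | 6% | 8% | 7.48 | 9.51 | 1.27 | 1.45 | 0.79 |

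The HR column comes from simulated Cox fits (400,000 patients per group) and is good to about 0.01. The other columns are analytic.

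**When the bias is small or absent.**
- Fixed 6-month course in both groups: HR stays 0.77, the control median is 7.2 (W = 24) to 7.9 (W = 180), and the ratio is about 1.30 to 1.33.
- No true effect, equal starts and practice: HR is 1.00 within simulation error.
- All patients kept and the progression-free censored: medians 8.0 and 10.4, HR 0.77, at every W.

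**A different assumed median.** With a control median of 6 and a true ratio of 1.30, therapy until progression gives control medians of 2.55 to 5.55 and ratios of 1.07 to 1.27 for W = 12 to 120. If some patients also stop for toxicity (0.02 per month), the attenuation lessens: at W = 24 the ratio is 1.18 instead of 1.13.

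**Scale against sampling error.** The largest shift in log HR is ln(0.91/0.77) ≈ 0.17. With d events per group, the SE of log HR is √(2/d), which is 0.45, 0.32 and 0.22 for an assumed d of 10, 20 and 40. The shift is below one SE in each case.

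**The case against.** The best defence is that the plan shows signs of expecting censored patients. Kaplan-Meier and reverse Kaplan-Meier make little sense otherwise, and the evaluability rule says nothing of completion. That is fair, but the censoring could belong to OS or to patients off treatment, and an exclusion acts before the evaluability rule. The text as written still removes patients on therapy. One could also read the criterion as *neither received nor completed*, which excludes only untreated patients and causes no bias, but then *completed* adds nothing to *received*.

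It can also be said that defining *completed* would be enough. That would make sites consistent, but a definition meaning that therapy has ended would leave the selection on outcome in place.

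The effect on the group comparison is modest. The HR moves only if there is a true effect and therapy runs until progression, and then by less than one SE at the assumed event counts. Nothing in the documents points to a short look-back. This stands, and it limits the weight of the point.

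Four stronger readings are tempting and not supported.

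- *The passages contradict each other.* An exclusion may narrow an inclusion; this is an undefined term, not a strict contradiction.
- *PFS could be biased upward because patients who progressed before finishing a planned course are dropped.* This fits *not yet* poorly. Because the criterion asks for at least one therapy, not first-line therapy, an early progressor who completed a later line stays in. A figure such as 6 + 8 = 14 months for the control median (6-month course) is therefore an upper bound and should not carry the claim.
- *The comparison is biased even with no true effect.* That would need start dates or regimens to differ by fusion status. Neither is a matching factor ("The two groups will be matched with respect to histological subtype, sex, age (+/-5 years), and pathological tumor-node-metastasis (TNM) stage"), but the documents suggest no particular imbalance.
- *The 30% verdict will be wrong.* That rule speaks of median survival and does not name PFS, so the link is conditional.

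**Conclusion.** The concern holds for the natural reading. Applied as written, the exclusion discards progression-free patients whom the planned methods can use. Where therapy runs until progression, it lowers the PFS medians and shrinks a true difference. The direction follows from the selection; the size does not follow from the documents. Under exponential PFS, an 8-month control median and uniform starts, it ranges from severe at a 24-month look-back to slight at 180 months, and it is also slight for fixed courses unless the look-back is short. If the 30% rule is applied to PFS, a true 50% increase would fall below it at W = 24 and 36 but not at 60 or more. This should be fixed; it does not by itself invalidate the comparison.

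**What to change.** 1. Delete *or completed* from the exclusion criterion, so that it agrees with inclusion item 4 and the evaluability rule.
2. State a PFS data cut-off date.
3. State that patients progression-free at cut-off, including those still on first-line therapy, count as having PFS information under both item 4 and the evaluability rule, and are censored at their last disease assessment before cut-off. Without this sentence the deletion alone may not bring them in, because neither clause says whether a censored time counts as available PFS.

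The cost is two words, one date and one sentence. One data field is probably needed as well: the data collection list has treatment, progression and death dates but no date of last disease assessment. The downside is a few more censored patients. Making the change before chart collection avoids going back for records that were wrongly left out.
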